3. STUDY DESCRIPTION

3.1 Study Design

This Phase 2 study will be an interventional, open-label, single arm trial where each patient is his/her own “intrapatient” control. All patients will receive a single █ mg/kg dose of pegsitacianine administered █ prior to standard of care (SOC) surgery. The study will be conducted in two Parts. Part 1 will enroll patients undergoing minimally invasive procedures (i.e., video-assisted thorascopic surgery [VATS] or robotic surgery). Part 2 will be opened at the discretion of the Sponsor and include patients undergoing open thoracotomy for the removal of their disease. [Note: Part 2 was not opened to enrollment.]

Patients will have a biopsy confirmed diagnosis, or a high clinical suspicion of a lung malignancy based on CT and/or PET imaging. A total of up to 40 patients will be enrolled in this trial. The sponsor reserves the right to perform an interim analysis following early enrollment (n ≤ 10 subjects) to determine the feasibility and benefit of pegsitacianine as an adjunct to SOC surgery.

The surgeon will attempt to perform their SOC resection of visible tumors. If the tumor is unable to be located under standard white light conditions, an appropriate near-infrared (NIR) imaging device may be used to aid in the location of the primary tumor. Localization of the primary tumor using NIR imaging in conjunction with pathology confirmed presence of disease will be considered a clinically significant event.

If the primary tumor is located using standard white light procedures, the tumor will be imaged using the NIR camera and removed as per standard of care (i.e., wedge, lobectomy, etc.). The primary resection will then be imaged (front, back and margins) on a piece of normal tissue within the surgical field at a distance from the specimen equal to the working distance of the camera system. Inspection and imaging of the resection margins will be performed using the NIR camera system. If an area of suspicion is observed, images will be captured of the area, at the working distance of the camera away from the margin and documented for future correlation to pathological findings. Similarly, the *in situ* resection margin on the lung will be imaged for signs or residual fluorescence that may correspond to disease left behind. If found, images will be captured prior to the excision of the margin (*in situ*) and following its resection on a piece of normal tissue (*ex situ*). Resection of the suspicious or fluorescent margin is at the discretion of the surgeon. This procedure is to be repeated if additional SOC nodules are planned for resection. An identical approach will be followed for any SOC lymph nodes collected during the procedure. Lymph node imaging will occur prior to and following the removal of the suspected lymph nodes.

Once SOC surgical resection is complete, the surgeon will use the NIR camera system to evaluate the thoracic cavity (i.e., chest wall, contralateral lung, bronchi, etc.) for indications of residual fluorescence. If additional fluorescent foci are observed, the area may be resected, at the discretion of the surgeon, for pathological confirmation of disease. Similar to the imaging of margin resections, the suspected area will be imaged prior to removal (*in situ*) and following resection (*ex situ*) on a piece of normal tissue within the thoracic cavity. Additional fluorescent lymph nodes, detected during the evaluation of the thoracic cavity, may also be collected and imaged both *in situ* and *ex situ* prior to being evaluated in pathology. Thus, each subject is their own "intrapatient" control.

Collected surgical specimens will be documented as called out by the surgeon. The fluorescence status of each specimen will then be correlated to the final pathology for each and the performance metrics of pegasitacianine will be tabulated.

3.2 Study Treatment

Each patient will be administered a █ mg/kg dose of pegasitacianine █

The volume of drug and total dose will vary by patient and will depend on the patient's body weight.

4. SAMPLE SIZE AND POWER CALCULATION

The sample size for this study will be 40 subjects. This sample size is based on historical experience with the proposed analysis. A sample size of 40 subjects will be sufficient for meeting the endpoints described herein.

5. ANALYSIS ENDPOINTS

5.1 Efficacy Endpoints

5.1.1 Clinically Significant Event Endpoints

Performance metrics will include the identification of a CSE detected by pegasitacianine. CSEs will include pegasitacianine detection of primary tumors otherwise undetectable using SOC procedures, detection of occult disease not otherwise known by the surgeon to exist (as synchronous disease), the detection of a positive surgical margin, and accurate identification of tumor negative SOC biopsies. A list of CSEs and their definitions is provided below.

- **Detection of Synchronous Disease** – identification of tumor-containing tissue due to pegasitacianine fluorescence, confirmed via histopathological analysis, that otherwise went undetected during pre-operative imaging (PET, CT, MRI) or by the surgeon during SOC surgery.
 - This occurs when a specimen that comes from the thoracic cavity or lymph nodes, is (1) collected via fluorescence and (2) is pathologically-confirmed as a tumor. Note that any specimen collected from the thoracic cavity following SOC will be considered to be collected by fluorescence.

- Detection of Positive Surgical Margin – following the completion of SOC surgery, the surgical fields will be examined for residual fluorescence. Detection of a positive surgical margin would be those specimens collected as a result of residual pegsitacianine fluorescence following the completion of SOC surgery that return a histologically positive for tumor outcome.
 - This occurs when a margin specimen (either from the primary tumor or a lung resection margin) (1) is collected via fluorescence and (2) is pathologically-confirmed as a tumor. Note that any lung resection margin collected will be considered to be collected by fluorescence.
- Identification/Localization of the Primary Tumor – during SOC surgery, the surgeon will examine the affected lung to locate the primary tumor. If the primary tumor is not visually apparent using standard imaging methods the surgeon may use the NIR imaging device to aid in localization. If the NIR imaging identifies and/or locates the primary tumor, which was undetectable using SOC approaches, this will be deemed a CSE.
 - This occurs when the primary tumor is not located using SOC approaches, and is instead identified using NIR imaging.
- Tumor Negative SOC Biopsies – during SOC surgery, the surgeon will collect tissue specimens that are suspicious for disease. If those samples do not demonstrate pegsitacianine fluorescence and are found to be devoid of tumor pathologically, those specimens would be included as a tumor negative SOC biopsy.
 - This occurs when any SOC sample (primary tumor, additional SOC specimen, or lymph node) that is collected that is found to be negative for tumor, and did not fluoresce during *ex situ* imaging.

A subject with any CSE will be considered a CSE responder.

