--	---

	metrics of pegsitacianine, the fluorescence status of each specimen will be correlated to the final pathology and results will be tabulated.
Endpoints	
Primary Endpoints: Discovery of a clinically significant event (CSE) at the level of the subject. CSEs may include detection of primary tumors that went undetected under white light, discovery of occult disease, positive margins detected by fluorescence that would have otherwise gone undetected, or tumor-negative SOC biopsies.
 
Secondary Endpoints: Secondary endpoints will evaluate the safety and toxicity of pegsitacianine, as well as performance metrics of the drug at the level of the collected specimens. The performance metrics will include:
 
 
• Sensitivity
 
• Specificity
 
• NPV
 
• PPV
 

Study Drug	mg/kg of pegsitacianine prior to surgery

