If the primary tumor is located using standard white light procedures, the tumor will be imaged using the NIR camera and removed as per standard of care (i.e., wedge, lobectomy, etc.). The primary resection will then be imaged (front and back) on a piece of normal tissue within the surgical field at a distance from the specimen equal to the working distance of the camera system. Inspection and imaging of the resection margins will be performed using the NIR camera system. If an area of suspicion is observed, images will be captured of the area at the working distance of the camera away from the margin and documented for future correlation to pathological outcomes. Similarly, the resection margin on the lung will be imaged for signs or residual fluorescence that corresponds to residual disease left behind. If found, images will be captured prior to the excision of the margin (*in situ*) and following its resection on a piece of normal tissue (*ex situ*). This procedure is also to be repeated if additional SOC nodules are planned for resection. An identical approach will be followed for the collection of any SOC lymph nodes collected during the procedure. Lymph node imaging will occur prior to and following the removal of the suspected lymph nodes.

Once SOC surgical resection is complete, the surgeon will use the NIR camera system to evaluate the thoracic cavity (i.e., chest wall, contralateral lung, bronchi, etc.) for indications of residual fluorescence. If additional fluorescent foci are observed, the area may be resected at the discretion of the surgeon for pathological confirmation of disease. Similar to the imaging of margin resections, the suspected area will be imaged prior to removal (*in situ*) and following resection (*ex situ*) on a piece of normal tissue within the thoracic cavity. Additional fluorescent lymph nodes, detected during the evaluation of the thoracic cavity, may also be collected and imaged both *in situ* and *ex situ* prior to being passed on to pathology.

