### 9.3 Rate of Clinically Significant Events

Determining the rate of clinically significant events (CSE) detected by pegsitacianine at the subject-level is the primary objective of this study. CSEs will include pegsitacianine detection of primary tumors otherwise undetectable using SOC procedures, detection of occult disease not otherwise known by the surgeon to exist, the detection of a positive surgical margin, and accurate identification of tumor negative SOC biopsies. A list of CSEs and their definitions is provided below.

- Detection of Synchronous Disease – identification of tumor-containing tissue due to pegsitacianine fluorescence, confirmed via histopathological analysis, that otherwise went undetected during pre-operative imaging (PET, CT, MRI) or by the surgeon during SOC surgery.
  - This occurs when a specimen that comes from the thoracic cavity or lymph nodes, is (1) collected via fluorescence and (2) is pathologically-confirmed as a tumor. Note that any specimen collected from the thoracic cavity following SOC will be considered to be collected by fluorescence.
- Detection of Positive Surgical Margin – following the completion of SOC surgery, the surgical fields will be examined for residual fluorescence. Detection of a positive surgical margin would be those specimens collected as a result of residual pegsitacianine fluorescence following the completion of SOC surgery that return a histologically positive for tumor outcome.
  - when a margin specimen (either from the primary tumor or a lung resection margin) (1) is collected via fluorescence and (2) is pathologically-confirmed as a tumor. Note that any lung resection margin collected will be considered to be collected by fluorescence.
- Identification/Localization of the Primary Tumor – during SOC surgery, the surgeon will examine the affected lung to locate the primary tumor. If the primary tumor is not visually apparent using standard imaging methods the surgeon may use the NIR imaging device to aid in localization. If the NIR imaging identifies and/or locates the primary tumor, which was undetectable using SOC approaches, this will be deemed a CSE.
  - This occurs when the primary tumor is not located using SOC approaches, and is instead identified using NIR imaging.

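### The counting rule for the synchronous-disease CSE leaves out its definition's otherwise-undetected condition, and the margin rule drops timing and presumes attribution, so already-known disease can count toward the primary endpoint

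*SAP*

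**What the plan says.** The primary endpoint is the proportion of subjects with any clinically significant event (CSE). Protocol 9.3 and SAP 5.1.1 describe each CSE type in two layers: a definition, then a sub-bullet stating when the event occurs.

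- **Synchronous disease, definition.** Histologically confirmed tumor found through fluorescence "that otherwise went undetected during pre-operative imaging (PET, CT, MRI) or by the surgeon during SOC surgery". The lead paragraph of Protocol 9.3 describes the category as "detection of occult disease not otherwise known by the surgeon to exist"; SAP 5.1.1 uses the same description and labels it synchronous disease.
- **Synchronous disease, counting rule.** A specimen that "comes from the thoracic cavity or lymph nodes, is (1) collected via fluorescence and (2) is pathologically-confirmed as a tumor". A note follows: "Note that any specimen collected from the thoracic cavity following SOC will be considered to be collected by fluorescence".
- **Positive margin, definition.** "those specimens collected as a result of residual pegsitacianine fluorescence following the completion of SOC surgery that return a histologically positive for tumor outcome".
- **Positive margin, counting rule.** "This occurs when a margin specimen (either from the primary tumor or a lung resection margin) (1) is collected via fluorescence" and is tumor on pathology. A note treats every lung resection margin as having been collected because of fluorescence.
- **Protocol Summary, Endpoints.** CSEs may include "positive margins detected by fluorescence that would have otherwise gone undetected".

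SAP 7.10.1.1 reports responders and each CSE type with Clopper-Pearson intervals. SAP Section 1 gives the SAP precedence over the protocol for analyses, and SAP Section 8 states that no deviations are planned.

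**The concern.** The trial has one arm, and each patient serves as his or her own control. The comparison is with what SOC would have found without the agent, so the otherwise-undetected condition is what makes a finding a benefit of the agent. If the rule that is programmed does not contain it, the CSE rate mixes new detection with confirmation of known disease.

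Two cases show the gap. In the first, a nodule reported on the pre-operative scan but not removed as part of SOC is taken from the thoracic cavity after SOC and proves malignant. It passes the synchronous-disease rule. In the second, a lung resection margin is re-resected because the surgeon felt tumor there, and it is positive. It passes the margin rule even if it did not fluoresce, because the note supplies the attribution.

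Protocol 9.1 says the study is meant to inform power calculations for later trials, so an inflated rate would carry forward.

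**Working it through.** The plan states no target CSE rate, power or alpha, so there is no figure of its own to reproduce. The check is mainly a comparison of texts, with a small calculation for scale.

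**1. Synchronous disease: definition against rule.**

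| Element | Definition | Counting rule |
|---|---|---|
| Tumor on pathology | yes | yes |
| Found because of fluorescence | yes | yes, but presumed for post-SOC thoracic-cavity specimens |
| Undetected on pre-operative imaging or by the surgeon | yes | absent |

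For a post-SOC thoracic-cavity specimen, pathology is the only test left. Lymph nodes have no such note, so for them the fluorescence test is real.

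**2. Positive margin: definition against rule.**

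| Element | Definition | Counting rule |
|---|---|---|
| Tumor on pathology | yes | yes |
| Collected because of residual fluorescence | yes | yes, but presumed for lung resection margins |
| After completion of SOC | yes | absent |
| Otherwise undetected | absent (Protocol Summary only) | absent |

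**3. Is the omission a drafting convention?** No. The primary-tumor rule in the same list keeps its counterfactual: the tumor was not located by SOC approaches and was identified by near-infrared (NIR) imaging instead.

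**4. Could the planned data repair it?** Only partly. The specimen listing in SAP 7.10.2.1 shows fluorescence in situ and ex situ for every specimen. It shows SOC-or-fluorescence collection only for primary, additional SOC and lymph node specimens, and has no item for pre-operative imaging status. For SOC nodes, Protocol 3.1 says "Lymph node imaging will occur prior to and following the removal of the suspected lymph nodes", and no written SOC plan is required before the camera is used.

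**5. Scale.** SAP 5.1.1 makes a subject with any CSE a responder. Let n be the number analyzed, a the subjects with a genuine CSE of any type, and b the subjects who respond only through already-known disease. The rate moves from a/n to (a + b)/n, a shift of b/n.

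- For n = 40 and b = 1, the shift is 1/40 = 2.5 points.
- Assumed a = 3, b = 0: 3/40 = 7.5%, exact 95% CI 1.6 to 20.4.
- Assumed a = 3, b = 3: 6/40 = 15.0%, exact 95% CI 5.7 to 29.8.
- SAP 6.3 restricts the Efficacy population. If n were 30 (an assumption), one such subject would add 1/30 = 3.3 points.

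A subject who already has another CSE is not in b and leaves the overall rate unchanged. The rate for the affected CSE type still rises unless that subject also has a genuine event of the same type.

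**The case against.** **The sub-bullet sits under a definition that still has the condition.** Nothing says it replaces that text, and the lead paragraph calls the category disease not known to the surgeon. A careful programmer might read the two together. This has some force, but the sub-bullet is the part written as a classification rule, with numbered tests and a presumption, and the neighboring primary-tumor rule restates its condition.

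**There are safeguards.** The thoracic sweep follows SOC, planned nodules are handled as SOC, and nodes carry a collection label. This stands as a partial proxy for disease missed by the surgeon; it says nothing about pre-operative imaging. A re-resection done for SOC reasons might also be filed as an additional SOC specimen, but the documents do not say so.

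**The definition's "or" is ambiguous.** If it means missed by either method, a lesion seen on a scan but missed at surgery qualifies. That narrows the gap without closing it.

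**Stronger readings a reader might infer.**

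- *The margin rule drops an otherwise-undetected condition from its own definition.* It does not, because that definition has none. The wording is only in the Protocol Summary, in a sentence about what CSEs may include.
- *Known disease always counts, or the intrapatient control is not applied at all.* The documents show only that known disease can count.
- *Every known lesion adds 2.5 points.* The endpoint is per subject, and one non-fluorescent, tumor-negative SOC node already makes a responder.
- *The SOC label on nodes is settled by the camera.* The Protocol Summary's surgery steps have nodes designated for SOC collection before they are imaged. What is missing is a record of that designation made before NIR use.

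**Conclusion.** The point holds in this form. For synchronous disease, the counting rule in both documents is wrong as written: it omits a condition of its own definition and, for post-SOC thoracic-cavity specimens, presumes the fluorescence attribution. For margins, the faults are the omitted post-SOC timing, the presumed attribution for lung resection margins, and a mismatch with the Protocol Summary.

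The size cannot be derived from the documents, which give no CSE rate and no frequency of already-known lesions. The 7.5% and 15.0% figures rest on assumed counts, on all 40 subjects being analyzed, and on the three added subjects having no other CSE. Where another CSE is common, the overall rate moves less and the distortion shows mainly in the per-type rates. Separate reporting and the CSE listing make the mix of types visible, but do not show which events were already known. In an unpowered pilot this calls for a correction to the rules; it does not undermine the design.

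**What to change.** Make the same changes in SAP 5.1.1 and Protocol 9.3.

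1. **Synchronous disease.** Add a third condition: the lesion or node had not already been identified on pre-operative imaging or by the surgeon during SOC. State whether "or" means missed by both or by either.
2. **Positive margin.** Restore the post-SOC timing, and require that the SOC assessment had not already judged the margin positive. This also brings the rule into line with the Protocol Summary.
3. **Attribution.** Replace the two presumptions with the actual reason for collection, recorded per specimen, and extend the SAP 7.10.2.1 listing to show it for margins and thoracic-cavity specimens, together with pre-operative imaging status.
4. **Reporting.** List specimens that fail these conditions as fluorescent but already known, and do not count them toward response.

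Where surgery is still to come, enter the SOC plan and the SOC margin assessment in the Imaging Workbook before NIR use. SAP 3.1 already notes that Part 2 was not opened, so some or all operations may be past. For those patients, classify from existing imaging reports and operative notes where available, and report how many specimens could not be classified. SAP 7.1 allows updates before database lock and requires a protocol amendment for method changes that may affect the primary conclusions.

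The cost is a small recording and classification burden, and a CSE rate that may be lower.

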5.1.2 Diagnostic Imaging Endpoints

Diagnostic performance of pegsitacianine will be assessed by calculating sensitivity, specificity, NPV, and PPV of pegsitacianine in detecting tumor containing tissue. The *ex situ* fluorescence status (any fluorescence vs. no fluorescence) of collected SOC and pegsitacianine guided specimens, as well as lymph nodes, will be compared to histological analyses of the collected specimens. Sensitivity and specificity for detecting tumor-containing tissue versus normal tissue

will be evaluated using tissue specimen fluorescence and the corresponding pathological outcomes.

True/false/negative/positive definitions are as follows:

- False positive is defined as fluorescence was observed on the sample but the sample was not found to have tumor via pathology.
- False negative is defined as no fluorescence was observed on the sample but the sample was found to have tumor via pathology.
- True positive is defined as fluorescence was observed on the sample and the sample was found to have tumor via pathology
- True negative is defined as no fluorescence was observed on the sample and the sample was found not to have tumor via pathology.

Pegsitaricaine sensitivity and PPV will be calculated using the following equations:

$$\text{Sensitivity} = \frac{\text{\# of True Positive Specimens}}{\text{\# of True Positive Specimens} + \text{\# of False Negative Specimens}}$$

$$PPV = \frac{\# \text{ of True Positive Specimens}}{\# \text{ of True Positive Specimens} + \# \text{ of False Positive Specimens}}$$

Pegsiraniline specificity values and NPV will be calculated using the following equations:

$$\text{Specificity} = \frac{\text{\# of True Negative Specimens}}{\text{\# of True Negative Specimens} + \text{\# of False Positive Specimens}}$$

$$NPV = \frac{\# \text{ of True Negative Specimens}}{\# \text{ of True Negative Specimens} + \# \text{ of False Negative Specimens}}$$

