7.10.2 Secondary Analyses

7.10.2.1 Analysis of Diagnostic Imaging

The positive predictive value, negative predictive value, sensitivity, and specificity (specimen level) will be calculated and summarized for each Part and overall. The summary will include the true/false negative/positive rate and number of specimens. Two-sided 95% confidence intervals will be calculated for each rate via Clopper-Pearson method.

A listing by subject and specimen showing the specimen type (primary tumor/ additional SOC specimen, lung resection margin, thoracic cavity, lymph node), attainment by SOC or fluorescence (if primary/ additional SOC/ lymph), pathology result, fluorescence *in situ* and *ex situ*, and fluorescence measures (MFI and TBR) will be provided.

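### Two notes in the primary endpoint credit every lung resection margin and every post-SOC cavity specimen to fluorescence, so a tumor found without an observed signal would count as detected by the agent

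*SAP*

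**What the plan says.** SAP 5.1.1 and Protocol 9.3 define four CSE types. SAP 5.1.1 then makes one event enough: "A subject with any CSE will be considered a CSE responder". Two of the types are at issue.

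- **Synchronous disease.** The headline definition is "identification of tumor-containing tissue due to pegasitacianine fluorescence, confirmed via histopathological analysis". The operational rule has two conditions: collection via fluorescence, and tumor on pathology. The note then adds: "Note that any specimen collected from the thoracic cavity following SOC will be considered to be collected by fluorescence".
- **Positive surgical margin.** The headline definition is "those specimens collected as a result of residual pegsitacianine fluorescence following the completion of SOC surgery", with tumor on histology. The same two conditions follow, and then the note: "Note that any lung resection margin collected will be considered to be collected by fluorescence".

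Both notes stand in both documents, so this is not a SAP departure from the protocol. Margins on the excised primary specimen are outside the margin note.

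On how these specimens arise, SAP 3.1 describes NIR inspection of the margins and the cavity, with excision when residual fluorescence is seen. It also says: "Resection of the suspicious or fluorescent margin is at the discretion of the surgeon".

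For the secondary endpoint, SAP 5.1.2 states: "False negative is defined as no fluorescence was observed on the sample but the sample was found to have tumor via pathology". The planned specimen listing in SAP 7.10.2.1 gives pathology and in situ and ex situ fluorescence for each specimen. It shows the route of collection only for some types: "attainment by SOC or fluorescence (if primary/ additional SOC/ lymph").

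**The concern.** The trial has one arm and each patient serves as his or her own control. For these two CSE types the only comparison is between what SOC surgery found and what fluorescence found. The notes fix the answer in advance for two specimen classes, so only pathology is left to decide the event.

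The resulting error has one direction. A tumor removed without a fluorescent signal can add an event but can never take one away. It also falls in the components that carry the claim of added detection, and Protocol 9.1 says the study is meant to inform power calculations for later studies.

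**Working it through.** **1. The rule applied to one specimen.** Take a lung resection margin, or a cavity specimen taken after SOC, with tumor on pathology and no fluorescence observed in situ or ex situ.

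| Rule | Test | Result |
|---|---|---|
| Headline definition, SAP 5.1.1 | Was fluorescence the reason for identification or collection? | No, so no CSE |
| Operational rule with note, SAP 5.1.1 | Condition 1 met by the note; condition 2 met by pathology | CSE, so responder |
| SAP 5.1.2 | No fluorescence ex situ, tumor present | False negative |

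The note contradicts the definition it belongs to, and the same specimen counts for the agent in the primary analysis and against it in the secondary one. By contrast, the tumor-negative SOC biopsy CSE in the same section does test ex situ fluorescence.

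The clash with SAP 5.1.2 is not by itself proof of a wrong count. A specimen that fluoresced in situ but was dark ex situ is a genuine fluorescence-guided find and still a false negative under 5.1.2. The miscount is confined to specimens with no observed signal.

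**2. The two notes compared.** The cavity note is limited to specimens taken after SOC, and the workflow describes cavity excision only for fluorescent foci. The margin note has no such time limit, although its headline definition does. A lung margin taken during SOC surgery is therefore covered. SAP 3.1 and the Protocol Summary also name suspicious margins as an alternative to fluorescent ones. The margin note is the weaker of the two.

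**3. Size.** The planned 40 patients (SAP 4, Protocol 9.1) rest on historical experience, with no formula, so there is no stated figure to reproduce. Counts below are assumptions; intervals are exact (Clopper-Pearson, SAP 7.10.1.1).

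- *One patient:* 1/40 = 2.5 points. With a smaller efficacy population, 1/30 = 3.3 and 1/20 = 5.0 points.
- *One component rate:* with 4 genuine cases, 4/40 = 10.0% (95% CI 2.8 to 23.7). Two deemed cases in patients without another event of that type give 6/40 = 15.0% (5.7 to 29.8). With no deemed case it stays at 10.0%.
- *Any-CSE rate:* suppose 10 patients respond without the deemed specimens, so 10/40 = 25.0% (12.7 to 41.2). Suppose two patients have a deemed dark tumor. If neither has another CSE, the rate is 12/40 = 30.0% (16.6 to 46.5). If one does, it is 11/40 = 27.5% (14.6 to 43.9). If both do, it stays at 25.0%.
- *Chance of at least one case in 40:* 1 − (1 − p)^40, where p is the assumed chance per patient. For p = 1%, 2.5% and 5% this gives 33%, 64% and 87%.

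**4. What the planned outputs show.** The SOC-or-fluorescence route is not listed for margin or cavity specimens, but fluorescence status and pathology are listed for every specimen. A reader could find a deemed case afterwards; the CSE count would still include it.

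**The case against.** The strongest defense is that the notes are coding conventions. The workflow describes cavity excision after SOC only when fluorescent foci are seen, and lung-margin excision when residual fluorescence is found. Tissue taken on ordinary surgical suspicion has its own class, the additional SOC specimen. That would explain why the route of collection is listed only for classes that can arise either way. The word *suspicious* in SAP 3.1 follows a passage on NIR inspection and may mean suspicious on NIR. This stands as an argument that cases will be uncommon, above all for cavity specimens. It does not rescue the rule, because the notes apply whether or not the workflow was followed, and the margin note reaches beyond it. If every such specimen does fluoresce, requiring the recorded status changes nothing.

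Four stronger readings are tempting and should not be drawn:

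- *That the primary rate will be materially inflated.* The documents give no frequency, and it may be zero.
- *That every dark, tumor-positive margin adds 2.5 points to the primary rate.* It does so only if the patient has no other CSE, and one dark, tumor-free SOC lymph node is enough to supply one. The rise from 10% to 15% is an example for a component, with assumed counts.
- *That the problem would be hidden.* The specimen listing exposes it.
- *That a decision would flip.* Protocol 9.1 says the study is not powered for hypothesis testing, and no success threshold is set for the CSE rate.

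**Conclusion.** The point holds as a defect in the endpoint rule. As written, the two notes let a tumor-positive margin or cavity specimen with no observed fluorescence count as a detection by the agent, against the definitions they are meant to apply.

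The effect is upward only. Each affected patient adds up to 2.5 points at 40 patients to the margin or synchronous-disease rate. That rate is reported separately under SAP 7.10.1.1, so another type of CSE in the same patient does not mask it. The any-CSE rate rises only for patients with no other CSE. How many patients are affected cannot be derived from the documents; the workflow points to few, more plausibly margins than cavity specimens.

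This should be fixed. The evidence does not show that it threatens the study's conclusions.

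**What to change.** In SAP 5.1.1 and Protocol 9.3, replace the two notes with this rule: a lung resection margin or cavity specimen counts as collected via fluorescence only if a fluorescent status was recorded for that site or specimen.

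- **Which status.** Use the in situ status that SAP 7.10.2.1 already lists. This keeps genuine finds that were dark ex situ.
- **Data capture.** Confirm that the Imaging Workbook and eCRF record it. The protocol describes one fluorescent or non-fluorescent call per specimen and does not clearly separate in situ from ex situ.
- **Missing values.** State the rule in advance, for example using the ex situ call when the in situ status is missing.
- **Reporting.** List tumor-positive margin and cavity specimens without recorded fluorescence separately, and do not count them as CSEs. The rate under the present notes may be shown as a sensitivity analysis.

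**Cost.** The SAP may be updated before database lock. Because the change touches the primary endpoint, SAP 7.1 calls for a protocol amendment where primary conclusions may be affected, so this is more than an edit of wording. If the Workbook already holds the in situ status, no new data are needed. The CSE rate may fall slightly.
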